In a 12 week, randomized, double-blinded, active controlled trial, with 9 month open-label extension of 250 participants with obesity; we will compare the weight loss response rate to obesity-phenotype-guided pharmacotherapy (intervention) vs. non-phenotype guided (randomly selected) pharmacotherapy (control) in patients with obesity. All 250 participants will be phenotyped and the medication selection will be randomly and double blinded (to physician, study team and participant) to the FDA-approved medicine suggested by the phenotype or to another FDA-approved medicine not suggested by the phenotype. A computer generated randomization schedule generated by the study statistician's office will be submitted to the Mayo Clinic CCaTS Research Pharmacy. Allocations will be concealed. This study will be blinded until data are transmitted to the statistician for data lock. All participants will receive a standard intense lifestyle intervention, which consists of 1 visit with registered dietitian. The phenotypic studies include (all performed in same day in the following order): Fasting blood collection, resting energy expenditure, gastric emptying

with meal for breakfast, behavioral questionnaires, and buffet meal test for lunch. Blood will be collected assessment of metabolomic biomarkers, gastrointestinal hormones, and DNA (blood and buccal swab). Stool samples for microbiome and bile acid. Saliva samples for assessment of metabolomic biomarkers. Participants will return to the CRTU to pick up medication based on the randomization and a personal fitness tracker. All participants will be seen at 4 and 12 weeks (+/- 4 days) (current standard in practice). Participants will keep a medication diary, which will have to be returned on the 12-week visit. A saliva, stool and fasting blood sample, and DEXA will be done at the 12-week visit. At the 12-week visit, participants will be unblinded to their "obesity-related phenotype" and they could contact their physician to continue a FDA-approved medication as part of clinical care. Study team will prospectively follow the patients' weight, waist circumference and use of obesity medications every 3 months for 1 year. In a sub-study, 40 participants will complete at baseline and at 10 weeks (+/- 2 weeks), a flexible sigmoidoscopy and a pCASL functional MRI; with the intention to study the effects of pharmacotherapy in gut mucosa and brain blood flow changes at baseline and after treatment.

Randomization and Allocation

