A computer generated randomization schedule generated by the study statistician's office will be submitted to the Mayo Clinic CCaTS Research Pharmacy. Randomization will be based on guiding pharmacotherapy based on the phenotype or randomly as current standard of care. Allocations will be concealed. This study will be blinded until data are transmitted to the statistician for data lock. All subjects will be given a verbal explanation of the study, provided time to read and study the written consent form and its information, given opportunities to ask questions and a copy of the consent form. Participants will be informed of their right to withdraw from the study at any time without prejudice to their clinical management now or in the future. Consent will be sought by one of the medical doctor investigators or the study coordinator, and consent will be documented by the participant's signature on the consent form. Mayo's Institutional

FIGURE 8: STUDY DESIGN - Randomized clinical trial to identify weight loss responders to obesity pharmacotherapy

Review Board will approve the process and protocol. All the members of multidisciplinary team for weight management (i.e. physicians, coordinators, clinical assistants, registered dietitians will remain blinded).

Selection Participants

We plan to study a cohort of 200 patients with obesity ($BMI > 30 \text{ kg/m}^2$) and an abnormal obesity-related phenotype. Participants will be recruited from the Mayo Clinic Weight Management and Nutrition Clinic when they are offered a medication for weight loss as standard of care for obesity; from our gastroenterology clinics; from our previous existing database of more than 1000 participants with obesity and from advertising and Mayo Clinic classifieds. Two hundred and fifty participants that agree to pharmacotherapy treatment will be invited to participate in the phenotypic assessment of their obesity, that will guide (or not) the pharmacotherapy.

Inclusion criteria

- Adults with obesity ($BMI > 30 \text{ Kg/m}^2$); these will be otherwise healthy individuals with no unstable psychiatric disease and controlled comorbidities or other diseases.
- Age: 18-75 years.
- Gender: Men or women. Women of childbearing potential will have negative pregnancy tests before each radiation exposure.
- Participant must have an abnormal phenotype based on testing done in visit 2.

Exclusion criteria

- a) Abdominal bariatric surgery

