Medication selection: Once the phenotype tests are completed the results will be filled in an algorithm to assist on the decision of the medication selection based on our previous data [3, 5, 11, 13]. The algorithm for phenotype selection will be based on the following decision tree (as figure below) 1) Participant will complete the ALL phenotype testing; 2) abnormal phenotype will be selected if participant meets criteria for one variable greater or lower than 90% of median (values described in table below); 3) if match to two or more abnormal (90% percentile) values, participant will be excluded; 4) if no abnormal ($<$ or $>$ 90%) value, the abnormal phenotype will be selected based on the value with $<$ or $>$ 75%; 5) if there are two or more abnormal values (75% percentile), patient will be excluded; 6) if participants do not have any abnormal value (based upon 90% of 75%) will be excluded.

TEST	Abnormal result					Example	Example	Example	Example
	Females		Males			1	2	3	4
	(90%)	(75%)	(90%)	(75%)	Female	Male	Male	Female	
Satiation (Ad libitum)	> 1065 kcal	> 894 kcal	> 1962 kcal	> 1376 kcal	1400 kcal	1000 kcal	1100 kcal	850 kcal	

Buffet Meal)								
Satiety (Gastric emptying SGE $T^{1/2}$)	< 97 min	< 101 min	< 76 min	< 86 min	102 min	80 min	105 min	110 min
Behavioral Traits (Questionnaires)	HADS > 9 points	HADS > 7 points	HADS > 10 points	HADS A > 7 points	5	4	9	3
Energy Expenditure (Resting EE)	< 93% predicted	< 96% predicted	< 88% predicted	< 94% predicted	102%	98%	95%	92%
Phenotype				-	Ab Satiety	Ab Satiety	Ab Psych	Ab E.E.

Once the decision is made on the “phenotype-guided” medication, pharmacy will assess whether patient is randomized to “intervention” or “control”. Based on the randomization, patient will pick up the prescription for 3 months.

Phentermine prescribed subjects will be recommended to involve into resistance training routines. During the 3 month visit, participants will be offered a prescription to continue the medication (if randomized to the intervention group) or switch to the phenotype guided medication (if randomized to the control group). Patients who continue obesity pharmacotherapy will be contacted every three months for one year to monitor their weight and comorbidities.

Control group: Pharmacotherapy for obesity

Standard of care pharmacotherapy for obesity recommends the following doses and regimen for weight loss:

- Phentermine: 15 mg oral daily

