The secondary end points will be percentage of responders (defined as number of participants who loss 5% or more of total body weight) compared to baseline in the obesity phenotype guided pharmacotherapy (intervention) group vs. standard of care at 4 and 12 weeks; percentage of responders with at least 10 and 15% at 12 weeks, and 10% at 6 months and 12 months; percentage of responders at 5%, 10% and 15%; percentage of responders within each obesity-phenotype group at 4 and 12 weeks; side effects of medications, pharmacogenomics role to weight loss, side effect and; changes in blood flow in the brain areas, and transcriptomic changes in colonic mucosa.; the performance of the PHENO-Test in predicting the obesity phenotype and the weight loss outcome based on the test when comparing phenotype-guided intervention vs. controls. In the open-label extension, we will assess the total body weight loss at 24 and 52 weeks in both groups.

Statistical Analyses: We propose a randomized, double-blinded, active controlled trial of 200 participants with obesity to compare effects of Intervention compared to controls in weight loss. The analysis will involve an ANCOVA models, with the response being actual weight change; the covariates to be considered include gender, and weight at baseline.

Sample size assessment and power calculation: The detectable effect size in weight loss between groups of interest (intervention vs. control) is given in the table below. In our recent pilot study [with Liraglutide 3.0 mg vs. placebo], the SD for the overall weight change (pre-post) observed was 2.8kg [32]. Using this SD, we have estimated the differences between groups that could be detected with approximately 80% power (2-sided α level of 0.05) for main effects. Thus, the sample size needed is 87 participants per group. In order to account for a maximum dropout rate of 13%, we will randomize 100 participants per group. An interim assessment will be done when 50% of the patients have completed the study for the purposes of assessing data quality and the power calculation assumptions. Specifically, that the weight change standard deviation is 2.8 and the dropout rate is 10-13%. No calculation of the treatment difference will be

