done at this assessment. Any suggested revision of the power and sample size calculation based on the standard deviation or dropout rate will be shared with the investigative team - possibly increasing the planned study enrollment. We have no intention of completing the study with less than the original sample size of 100 per group. In the subaim, we will use an ANCOVA to study 20 participants with phenotype-guided pharmacotherapy and compared to 20 participants randomly assigned pharmacotherapy adjusting for their baseline value as a covariate. Additionally, we will study the changes of each drug on treatment compared to baseline using a paired t-test. We noticed a 20% withdrawal rate during the study, we propose to extend to 250 participants enrolled and randomized to reach the 100 participants per group (total of 200 participants) who have completed the study.

Mean difference (Δ) of total body weight loss in controls group (mean average 6.1 kg) vs. intervention group.	Intervention (# of participants)	Control (# of participants)
Mean difference of 10% [6.7 vs. 6.1kg)	343	343
Mean difference of 20% [7.3 vs. 6.1kg)	87	87
Mean difference of 30% [7.9 vs. 6.1kg)	39	39

Anticipated results and significance:

Our study individualizes obesity treatment to maximized pharmacotherapy outcome based on phenotyping obesity at baseline.

Potential pitfalls, precautions taken, and alternative strategies:

- a. Feasibility - Given high volume of patients interested in weight loss, we are confident we will recruit sufficient participants for these studies that involve only noninvasive tests and standard of care treatment.
- b. Statistical power has been addressed with appropriate sample sizes to demonstrate a difference in weight change on NBSR with and with phenotype vs. placebo.

REFERENCE:

1. Apovian, C.M., et al., *A randomized, phase 3 trial of naltrexone SR/bupropion SR on weight and obesity-related risk factors (COR-II)*. *Obesity*, 2013. **21**(5): p. 935-43.
2. Pi-Sunyer, X., et al., *A Randomized, Controlled Trial of 3.0 mg of Liraglutide in Weight Management*. *The New England journal of medicine*, 2015. **373**(1): p. 11-22.
3. Acosta, A., et al., *Quantitative gastrointestinal and psychological traits associated with obesity and response to weight-loss therapy*. *Gastroenterology*, 2015. **148**(3): p. 537-546 e4.

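### No stratification by phenotype or sub-study is described, no concealed route to the 20 versus 20 sub-study is given, and phenotype is missing from both ANCOVAs

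*Combined protocol and SAP*

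**What the plan says.** Under Randomization and Allocation: "A computer generated randomization schedule generated by the study statistician's office will be submitted to the Mayo Clinic CCaTS Research Pharmacy", then "Randomization will be based on guiding pharmacotherapy based on the phenotype or randomly as current standard of care" and "Allocations will be concealed". Neither this section nor Study Design mentions a stratification factor, a block size or a list for the sub-study.

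Medication selection gives the order of events. The phenotype-guided drug is decided first; then "pharmacy will assess whether patient is randomized to" intervention or control. The phenotype is therefore known before the arm is applied.

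Study Design sets the sub-study size: "In a sub-study, 40 participants will complete at baseline and at 10 weeks (+/- 2 weeks), a flexible sigmoidoscopy and a pCASL functional MRI". The sample-size text under General Principles of Statistical Analyses then plans to analyse "20 participants with phenotype-guided pharmacotherapy and compared to 20 participants randomly assigned pharmacotherapy", by ANCOVA adjusted for the baseline value. No rule says how that split comes about. The secondary endpoints include "percentage of responders within each obesity-phenotype group at 4 and 12 weeks".

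The covariates named for the primary ANCOVA are gender and baseline weight. Phenotype is in neither model.

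**The concern.** Phenotype is probably the baseline factor that matters most to this trial's hypothesis. It fixes which of four drugs a guided participant receives. The preliminary data for Sub-aim 1 also tie it to the sub-study readouts: hypothalamic blood flow at maximal fullness (p=0.02), colonic mRNA for GLP-1 (p=0.01) and PYY (p=0.04), and left nucleus accumbens flow 30 minutes after maximal fullness (p=0.015).

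With only 40 people over four phenotypes, the two arms can easily differ in phenotype mix. A difference in blood flow or mucosal expression would then be hard to read, because part of it could reflect who was in each arm. Neither the described allocation nor the models guard against that.

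The 20 versus 20 plan raises a second question. A subset of 40 entering without regard to arm seldom splits exactly in half, so the plan should say who steers the split and how concealment is kept.

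**Working it through.** **The plan's own figure.** The documents give no figure for balance. The sample size does reproduce, which confirms the inputs used below. With SD 2.8 kg, difference 1.2 kg, two-sided 0.05 and 80% power, n = 2(1.960+0.842)² × 2.8²/1.2² = 85.5, so 86 per group by the normal formula. The t-test solution is 86.4, rounded up to the stated 87.

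**Chance of exactly 20:20 among 40.**
- Simple randomisation, binomial(40, 0.5): 12.5%.
- 40 drawn from 100:100: 14.0%. From 125:125: 13.7%. (The documents give both 100 per group and 250 randomised; equal arms are assumed.)
- The 95% range is 14:26 to 26:14 in all three cases.
- Enrolling regardless of arm until both arms hold 20 takes 45 people on average, with an 88% chance of being done by 50.

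**Cost of unequal arm sizes.** The standard error relative to 20:20 is √[(1/a + 1/(40−a))/(1/20 + 1/20)].

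| Split | Relative standard error |
|---|---|
| 18:22 | 1.005 |
| 16:24 | 1.021 |
| 15:25 | 1.033 |
| 14:26 | 1.048 |

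**Phenotype balance in the sub-study.** Assumption: 10 members in each of four phenotypes.
- Simple randomisation: one given phenotype splits 7:3 or worse with probability 0.344. For at least one of four, 1 − (1−0.344)⁴ = 0.81.
- Arms fixed at 20:20: one given phenotype 0.273 (hypergeometric); at least one of four 0.64 (exact count over all allocations).

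**Phenotype balance in the main trial.** Assumption: 50 in each of four phenotypes, 200 in all.
- Simple: one given phenotype splits 30:20 or worse with probability 0.203. At least one of four: 1 − (1−0.203)⁴ = 0.60.
- Arms fixed at 100:100: one given phenotype 0.141; at least one of four 0.40.
- Unequal strata of 56, 56, 68 and 20 (28%, 28% and 34% from the preliminary cohort, remainder assumed to be energy expenditure), arms fixed: about 56% for at least one 60:40 split or worse, driven by the stratum of 20.

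**What a phenotype imbalance does.** If one phenotype's mean outcome differs by D from the others, the unadjusted difference between arms shifts by D times the difference in that phenotype's share.
- Sub-study, 7:3 within 20:20: shares 7/20 = 35% and 3/20 = 15%, so the shift is 0.20 D. With D equal to one SD of the readout (assumed), that is 0.2 SD. The detectable difference at 80% power is 2.80 × √(1/20+1/20) = 0.89 SD.
- Main trial, 30:20 within 100:100: shares 30% and 20%, so 0.10 D. For D between 1 and 3 kg (assumed range; the documents give no value), the shift is 0.1 to 0.3 kg against the 1.2 kg target.

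These shifts average zero over randomisations.

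**Within-phenotype power.** For 1.2 kg in a stratum of 50, power is 33% at 25:25 and 32% at 20:30.

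**The case against.** The documents are silent; they do not say that allocation is simple or unstratified, and the study-design figure is not available. A reader might infer that the schedule is unstratified. The text supports only that no stratification is described. This stands.

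A reader might also infer that 20 versus 20 can be reached only by breaking concealment. The documents do not support that. The pharmacy holds the schedule, so it or the statistician's office could run a separate list or arm caps while the clinical team stays blinded. Modest over-enrolment would also do it, although someone with access to the schedule must say when to stop. No text describes choosing participants by their allocation. What remains is that no mechanism is stated.

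Exact equality is not needed either. ANCOVA tolerates unequal arms, and the standard error rises by only 0.5% at 18:22 and 5% at 14:26. This stands.

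Nor does chance imbalance invalidate the within-phenotype comparisons. Arms remain randomised within each phenotype, and the small stratum size limits these comparisons far more than imbalance does. This stands too. The secondary endpoint is also worded as a percentage within phenotype, without a named test.

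The 81% and 60% hold only under simple randomisation, which the documents do not state; hence the pairing with 64% and 40%.

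Finally, the sub-aim ANCOVA adjusts for the baseline value, which absorbs part of any phenotype difference already present at baseline. It does not absorb differences in change on treatment, and those are what a phenotype-determined drug would be expected to produce.

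**Conclusion.** The point holds as a gap in balance and precision, and it does not threaten the validity of the randomised comparisons. No stratification or blocking by phenotype or sub-study participation is described. No concealed mechanism is given for the planned 20 versus 20, and phenotype is absent from both models.

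The consequence falls mainly on the sub-study, where a 7:3 or worse split in at least one phenotype is more likely than not (about 64% to 81%). In the main trial a 30:20 or worse split in at least one phenotype has a chance of about 40% to 60%, and its effect on the primary comparison is modest. These figures rest on assumed equal phenotype sizes (10 and 50); the lower figure of each pair assumes fixed arm totals, the upper one simple randomisation. The precision gained by adjusting for phenotype cannot be given, because the documents do not say how much outcome variance phenotype explains.

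It is more than a missing detail, because the factor is measured in everyone, is known before the arm is looked up, and can be used at almost no cost.

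**What to change.** 1. Add assigned phenotype (four levels) as a covariate in the primary and sub-aim ANCOVAs. This can be done whatever the recruitment status, provided it is fixed before unblinding. It uses three degrees of freedom: residual degrees of freedom fall from 37 to 34 in the sub-aim model with 40 people (intercept, arm, baseline value), and from 196 to 193 in the primary model with 200 (intercept, arm, gender, weight).
2. State the randomisation method in use, including block sizes and any strata. If the schedule is already stratified, say so.
3. For participants still to be randomised, use permuted blocks held by the pharmacy and stratified by assigned phenotype. Record sub-study consent before allocation and use it as a second stratum, or give the sub-study its own list. About 20:20 then results without study staff consulting the allocation.
4. State that the sub-study analysis does not depend on exactly equal arms.

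The cost is a new list from the statistician's office. Eight strata, with about 10 people in each sub-study cell, will leave some incomplete blocks, so balance will be close but not exact, and dropout can still disturb it among completers. The sample size, procedures and blinding do not change.

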In July 2012, the FDA voted for approval of phentermine (3.75–15mg/d) plus extended release topiramate (23–92mg/d) as an adjunct to diet and physical activity for treatment of obesity among adult individuals with $\text{BMI} \geq 30\text{kg/m}^2$ or $\text{BMI} \geq 27\text{kg/m}^2$ with at least one obesity-related comorbid condition. The drug will carry a warning of potential increased risk for orofacial clefts in neonates exposed to topiramate during the first trimester of gestation and will be subject to a Risk Evaluation and Mitigation Strategy (REMS) that will restrict prescribing to trained clinicians, will require effective contraception and monthly pregnancy tests for reproductive age women, and will restrict dispensing to specific mail-order pharmacies. The company is also required to carry a long-term cardiovascular outcomes trial. No randomized pediatric studies have as yet been reported. Noteworthy, the high dose of PhenTop was associated with a mean weight loss of 9.8%; however, only 48% of patients lost $>10\%$ of their body weight, and 30% of patients lost $<5\%$ of their body weight (Figure 1). The high variability of weight loss response to treatment with PhenTop is unclear.

Lorcaserin (Belviq®): The second medication approved by the FDA in 2012 for chronic weight management is lorcaserin[26]. It is a serotonin receptor agonist thought to reduce food intake and increase satiety by selectively activating receptors on anorexigenic POMC neurons in the hypothalamus. At the recommended dose, lorcaserin selectively binds to 5-HT2C receptors instead of 5-HT2A and 5-HT2B receptors, which are associated with hallucinations and cardiac valve insufficiency respectively [27]. The recommended dose of lorcaserin is 10 mg twice daily. The medication should be discontinued if $\geq 5\%$ weight loss is not achieved after 12 weeks (Figure 2)[6].

[figure not shown]

Figure 2: Effects of Lorcaserin on Body weight. The proportions of patients who lost 5% or more or 10% or more of their baseline body weight at 1 year are shown [6].

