- b) Positive history of chronic gastrointestinal diseases, or systemic disease that could affect gastrointestinal motility, or use of medications that may alter gastrointestinal motility, appetite or absorption, e.g., orlistat, within the last 6 months.
- c) Significant untreated psychiatric dysfunction based upon screening with the Hospital Anxiety and Depression Inventory (HAD), and the Questionnaire on Eating and Weight Patterns (binge eating disorders and bulimia). If such a dysfunction is identified by an anxiety or depression score > 11 or difficulties with substance or eating disorders, the participant will be excluded and given a referral letter to his/her primary care doctor for further appraisal and follow-up.
- d) Hypersensitivity to any of the study medications.
- e) No contraindications to the FDA-approved medications: Phentermine-Topiramate Extended Release; Phentermine; Oral naltrexone extended-release/bupropion extended-release (NBSR; Contrave[®], Mysimba[™]); and Liraglutide (Saxenda[®]).
- f) Participants who meet the following criteria:
 - a. No match to any phenotype based upon 90th and 75th percentile criteria; or
 - b. Matches 2 or more phenotype based upon 90th percentile criteria; or
 - c. No match to phenotype based on 90th percentile criteria and 2 or more match to phenotype based upon 75th percentile criteria
- g) Sub Study specific exclusion criteria
 - a. Any contraindications to MRI
 - b. Claustrophobia

Anthropometrics and phenotype studies

Anthropometrics Measurements: will be taken of hip-waist ratio, height, weight, blood pressure, pulse at baseline, randomization day and week 12.

Phenotype studies at baseline:

Participants will attend the Mayo Clinic Clinical Research and Trials Unit after an 8-hour fasting period, and the following validated quantitative traits (phenotypes) will be measured at baseline:

- o) The DEXA scan (dual energy x-ray absorptiometry) will measure body composition.
- p) Resting energy expenditure: was assessed by indirect calorimetry with a ventilated hood (Parvo Medics, Sandy, UT).

- q) Gastric emptying (GE) of solids by scintigraphy: The primary endpoint is gastric half-emptying time (GE $t_{1/2}$) [3, 51, 52].
- r) Appetite (hunger level) by visual analog score fasting and after standard meal for GE and prior to the Satiation test [3].

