f. Exercise behavior - The Exercise Regulations Questionnaire (BREQ-3)[65] and its subsequent modifications have become the most widely used measures of the continuum of behavioural regulation in exercise psychology research. It has been used either as a multidimensional instrument giving separate scores for each subscale, or as a unidimensional index of the *degree of self-determination*.

g. Barriers to Increasing Physical Activity Participation - Barriers to Being Active Quiz, *What keeps you from being more active?*[66].

h. Three Factor eating questionnaire is 51-item questionnaire, validated, to assess for emotional eating disorders and food cravings.

i. Bowel Disease Questionnaire

Standard of Care:

All participants will receive standard of care which consists of 1) Intense lifestyle intervention, behavioral evaluation and treatment, and a medication as part of the regular clinic management for obesity.

Intense Lifestyle Intervention and Behavioral Treatment

All the participants will meet the multidisciplinary team which consists of an Obesity Expert physician and a CRTU registered dietitian nutritionist as standard of care in our clinical practice. These appointments will be scheduled in the CRTU. All participants will be guided to 1) Nutrition: Reduce dietary intake below that required for energy balance by consuming 1200calories per day for women and 1400calories per day for men; 2) Physical Activity: reach the goal of 10,000 steps or more per day; 3) Exercise: reach the goal of 150 minutes or more of cardiovascular exercise/week; 4) Limit consumption of liquid calories (i.e. sodas, juices, alcohol, etc.). All participants will receive a personal fitness tracker, where their activity and calories will be tracked. This information will be given in a booklet format.

[figure not shown]
Pharmacotherapy for obesity

Pharmacotherapy for the treatment of obesity can be considered if a patient has a body mass index (BMI) $\geq 30 \text{ kg/m}^2$ or BMI $> 27 \text{ kg/m}^2$ with a comorbidity such as hypertension, type 2 diabetes, dyslipidemia and obstructive sleep apnea[16]. Medical therapy should be initiated with dose escalation based on efficacy and tolerability to the recommended dose. We do an assessment of efficacy and safety at 4 weeks. In both groups, medications will be assessed for drug interactions and potential side effects as standard of care.

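### Pregnancy testing is tied only to radiation exposure, so the visible protocol omits the contraception and monthly testing that its own background says phentermine-topiramate ER requires

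*Combined protocol and SAP*

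**What the plan says.** - **Inclusion criteria (Selection Participants).** Men and women aged 18 to 75 may enter. The one pregnancy provision reads: "Women of childbearing potential will have negative pregnancy tests before each radiation exposure".
- **Background, Phentermine-Topiramate Extended Release.** The drug carries a "warning of potential increased risk for orofacial clefts in neonates exposed to topiramate during the first trimester of gestation", and its risk programme "will require effective contraception and monthly pregnancy tests for reproductive age women".
- **Control group and Intervention group.** Phentermine-topiramate ER 7.5/46 mg daily is the guided drug for the satiation phenotype. It is also on the list from which control drugs are drawn at random.
- **Study Design.** Participants come back after phenotyping to collect the drug and are seen at weeks 4 and 12, within 4 days either way. On radiation during treatment it says: "A saliva, stool and fasting blood sample, and DEXA will be done at the 12-week visit".
- **Medication selection.** "Based on the randomization, patient will pick up the prescription for 3 months".
- **Exclusion criteria, item e.** "No contraindications to the FDA-approved medications: Phentermine-Topiramate Extended Release; Phentermine", followed by the other two drugs. Standing in an exclusion list, this is worded the wrong way round, though the intent is clear.
- **Pharmacotherapy for obesity.** "In both groups, medications will be assessed for drug interactions and potential side effects as standard of care". The same section places an efficacy and safety assessment at week 4.

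**The concern.** The protocol records a teratogenic warning and a two-part precaution for one of its four drugs. Its operative criteria then contain only a rule aimed at a different hazard, radiation. Testing before radiation follows the imaging schedule, and imaging falls at the two ends of treatment. A site that follows the text exactly would schedule no pregnancy test between the baseline imaging and the week 12 DEXA, and would ask for no contraception.

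What is at stake is participant safety. A woman who conceives early in treatment could take topiramate during the first trimester, which is the exposure the warning concerns, with no scheduled test to detect the pregnancy until about week 12. The primary endpoint, sample size and analysis are not affected.

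**Working it through.** The protocol gives no figure of its own to reproduce here, so the check compares schedules.

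**1. When the radiation rule triggers a test.** Gastric emptying scintigraphy and DEXA are done at baseline, and DEXA again at week 12. The week 10 sub-study uses MRI and sigmoidoscopy, which trigger no test. Taking DEXA as a radiation exposure (an assumption):

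| Time | Under the stated rule | Under monthly testing |
|---|---|---|
| Baseline phenotyping | test | – |
| Drug pick-up (week 0) | none | test |
| Week 4 (visit exists) | none | test |
| Week 8 (no visit) | none | test |
| Week 12 | test | test |

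If DEXA did not count, there would be no test during treatment at all.

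**2. Length of the gap.** Counting the 12 weeks from drug start: 12 × 7 = 84 days, and ± 4 days gives 80 to 88 days (11.4 to 12.6 weeks). The time from the baseline test to drug pick-up is not stated and adds to this.

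**3. Whether other provisions fill the gap.**
- Scintigraphy is part of the phenotyping that every participant must complete, so a negative baseline test is in effect an entry condition.
- Item e, read as intended, would also exclude a woman known to be pregnant, but it does not provide for contraception or repeat testing.
- The physician's review of the selected drug (Control group section) refers back to the inclusion and exclusion criteria, so it adds no test.
- The week 4 assessment names no pregnancy test.

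**4. How many women might be concerned (illustration only).** Assume 1:1 allocation.
- The satiation share p comes from the Hungry Brain Phenotype section: 46/165 = 0.279 or 68/163 = 0.417. These cohorts were not filtered for mixed phenotypes as the trial will be.
- With 250 randomised (125 per arm), the intervention arm gives 125p = 34.8 or 52.1.
- Controls drawn evenly from the three non-suggested drugs give 125(1 − p)/3 = 30.1 or 24.3. Drawn evenly from all four, they give 125/4 = 31.25.
- Totals on the drug are 64.9 or 66.1 at p = 0.279, and 76.4 or 83.4 at p = 0.417, so about 65 to 83.
- With 100 per group, which the sample size section also states, the same formulas run from 27.9 + 24.0 = 51.9 to 41.7 + 25 = 66.7.
- The share of women of childbearing potential is not in the documents. At an assumed 20% to 60%, the extremes are 51.9 × 0.2 = 10.4 and 83.4 × 0.6 = 50.0, so about 10 to 50 women.

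**The case against.** The strongest reply is that these duties attach to the approved drug whether or not the protocol repeats them. The background says the risk programme restricts prescribing and dispensing, and the trial presents its drugs as standard care. That account is written in the future tense about a 2012 approval, and the documents do not show which terms applied during the trial. Contraception and pregnancy rules may also stand in the consent pages or the design figure, neither of which is shown. This has force. It means one cannot say that women in the trial went without these precautions. It does not change what the visible criteria say, or that they fall short of the requirement the protocol itself reports.

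A reader might go further in four ways that the documents do not support.

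- **That pregnant women could be enrolled.** The baseline test and item e, read as intended, largely cover entry.
- **That three months of drug are handed over at once with no refill prompt.** The text speaks of a three-month prescription and does not describe how it is filled.
- **That the blind forces the rule on every woman.** Both arms receive phentermine-topiramate ER, so a test prompted by that drug does not by itself reveal the arm. Drug identity is already partly visible: liraglutide is injected, naltrexone/bupropion is four tablets a day, and no double-dummy is described.
- **That exposure through most of the first trimester is likely.** A pregnancy may be noticed at or after the week 4 assessment. The background also reports 19 pregnancies carried to term in the drug's studies without congenital abnormalities, so the absolute risk may be small.

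**Conclusion.** The point holds as a gap in three items: contraception, a test at drug start, and testing on treatment. For a drug used in both arms, the visible protocol schedules no pregnancy test for 80 to 88 days after drug start, where its own background calls for monthly tests, and it sets no contraception requirement. This rests on counting DEXA as radiation, on timing week 12 from drug start, and on the missing consent pages and figure not already supplying the rules. The estimate of 10 to 50 women depends on an assumed share of childbearing potential; the conclusion does not depend on it. This is a low-cost participant-safety improvement with no effect on the statistical design.

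**What to change.** Amend the inclusion criterion along these lines: women of childbearing potential must not be pregnant, must agree to effective contraception while on study drug, and must test negative ahead of every radiation procedure, on the day drug is first dispensed, and at weeks 4 and 8 (a home test is acceptable at week 8). Study drug stops after a positive test.

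This is needed at least for women on phentermine-topiramate ER. Applying it to all women of childbearing potential is the simplest way to run it, because no drug-specific calls are needed; protecting the blind is a secondary benefit. If the consent form or design figure already holds these rules, copy them into the criteria. As an editorial correction, reword item e as: any contraindication to any of the study medications.

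The cost is up to three urine tests per eligible woman. Applied to all such women at the assumed 20% to 60% of 250, that is 250 × 0.2 × 3 = 150 to 250 × 0.6 × 3 = 450 tests. The week 4 visit exists, so only one week 8 contact is added. The criterion and consent text change; sample size and analysis do not.
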